7.4.2.3 Infusion Interruptions and Rate Changes

The following parameters will be summarized:

- Number of participants with at least one dose infusion interruption, number of infusion interruptions per participant and the reason for interruption.
- Number of participants with at least one IV infusion rate reduction, number of IV infusion rate reduction per participant and the reason for reduction

7.4.2.4 Dose Reductions/Escalation

There will be no dose escalations or reductions of nivolumab allowed.

7.4.3 Concomitant Medications

Concomitant medications, defined as medications other than study medications which are taken at any time on-treatment (i.e. on or after the first day of study therapy and within 100 days following the last dose of study therapy), will be coded using the WHO Drug Dictionary.

The following summary tables will be provided:

- Concomitant medications (participants with any concomitant medication, participants by medication class and generic term).
- Median and range of corticosteroids

A by-participant listing will accompany the tables.

7.5 Efficacy

Unless specifically mentioned, all efficacy analyses will be performed by two cohorts separately.

7.5.1 Primary analysis on BICR-assessed ORR

The BICR-assessed ORR will be summarized by cohort for all treated participants by a binomial response rate. The Clopper-Pearson method¹ will be used to estimate the two-sided 95% confidence interval.

Best overall response (BOR) will be summarized by response category (CR, CRu, PR, SD, PD, Non-evaluable, and not reported).

To assess tumor response kinetics, time to response will be analyzed using the KM methodology for all treated participants by cohort. Kaplan-Meier curve will represent the cumulative rate of response over time. For the non-responders, time to response will be censored at the maximum time to response + 1 day of all participants in that cohort.

The BICR-assessed DOR will be summarized by cohort for participants who achieve PR, CRu or CR using the Kaplan-Meier product-limit method. Median values of DOR, along with two-sided 95% CIs (based on the log-log transformation) and range, will also be calculated.

The following participant-level graphics will also be provided by cohort:

- For the responders only, time courses of the following events of interest will be graphically displayed: tumor response, tumor progression, last dose received, and death.
- For response evaluable participants, a waterfall plot showing the best reduction in target lesion will be produced. A spider plot showing the percentage of tumor size changes over time will also be produced.

The efficacy assessment slit lamp examination including the CNS ocular involvement over time relative to the 1st and the last doses will be listed. This may only include patients with CNS ocular involvement at baseline.

7.5.2 Secondary Efficacy Endpoints

7.5.2.1 PFS assessed by BICR

The BICR-assessed PFS assessment will be summarized descriptively by cohort using the Kaplan-Meier (KM) product-limit method for each cohort. Median values of PFS, along with two-sided 95% CIs (based on the log-log transformation), will also be calculated.

The BICR-assessed PFS rates at 3 and 6 months will be estimated using KM estimates on the PFS curve. PFS rates at 9, 12, 18, 24, 36 months may also be estimated depending on whether minimum follow-up will be longer than or equal to timepoint to generate the rate. Associated two-sided 95% CIs will be calculated.

The source of the BICR-assessed PFS event (death vs. progression) will be summarized. The status of participants who are censored in the PFS Kaplan-Meier analysis will be tabulated using following categories:

- On-study (on treatment or progression-free in follow-up).
- Off-study: (lost to follow-up, withdraw consent other).
- Received subsequent anti-cancer therapy.

PFS assessed by investigator will be analyzed similarly to the BICR assessed PFS.

7.5.2.2 ORR, BOR, TTR and DOR by investigator

The ORR, BOR, TTR and DOR assessed by investigator will be analyzed similarly to the same endpoints assessed by BICR.

7.5.2.3 Overall Survival (OS)

The OS curves will be estimated using the Kaplan-Meier (KM) product-limit method. Two-sided, 95% confidence intervals for median OS will be constructed based on a log-log transformed CI for the survivor function $S(t)$.

Survival rates at 3, 6, 9, 12, 18, 24, 36 months may also be estimated using KM estimates on the OS curve for each cohort. Minimum follow-up must be \geq timepoint to generate the rate. Associated two-sided 95% CIs will be calculated using the Greenwood's formula for variance derivation and on log-log transformation applied on the survivor function $S(t)$.

The status of participants who are censored in the OS Kaplan-Meier analysis will be tabulated using following categories:

- On-study (on-treatment or in follow-up).
- Off-study (lost to follow-up, withdraw consent, etc.).

7.5.2.4 Efficacy Analyses for Both PFS and OS

Participant Follow-up

The minimum follow-up will be reported. The minimum follow-up is defined as the time interval between the last patient's first dosing date of the considered cohort and the clinical cutoff date.

The extent of follow-up defined as the time between first dosing date and last known date alive (for participants who are alive) or death date (for participants who died) will be summarized descriptively (median, min, max) for all treated participants.

The currentness of follow-up, defined as the time between last OS contact (i.e., last known date alive or death date) and data cut-off date, will be summarized. Participants who died before data cut-off date will automatically have zero value for currentness of follow-up. For participants with last known date alive after data cut-off date, they will have zero value for currentness of follow-up as well. The currentness of follow-up will be categorized into the following categories: 0 days, 1-3 months, 3-6 months, 6-9 months, 9-12 months and \geq 12 months.

Follow-Up Therapy

The following information pertaining to subsequent therapies will be summarized:

Number and percentage of participants receiving subsequent therapies including:

- Chemotherapy by drug name.
- Immunotherapy (anti-PD1 agents, anti-CTLA4 agents and others, by drug name).
- Other investigational agent by drug name.
- Surgery.
- Radiotherapy.
- Autologous transplant
- Allogeneic transplant

A participant listing of follow-up therapy will be produced for participants who had any subsequent therapy.

By-subject listings will be provided for study related procedures including eye fundus examination, eye stereo color fundus photography, lumbar puncture, and lymphoma pet scan.

For subjects who underwent subsequent allogeneic transplant, by-subject listings will be provided with the following information: transplant characteristics, best response to transplant, GVHD, characteristics of acute GVHD and other transplant complications.

7.5.2.5 Efficacy for Participants Treated Beyond Progression

Individual time course of tumor burden change from baseline in target lesions, per investigator, will be generated for nivolumab participants treated beyond progression (spider plot).

The duration of treatment and number of doses beyond progression will be summarized.

7.5.3 *Subset Analyses*

The influence of enrolment prior versus after protocol amendment 9 and the influence on high versus lowdose of dexamethasone prior to the first dose of nivolumab on the efficacy measures will be evaluated descriptively by analyzing the following efficacy endpoints on each subset:

- BICR-assessed best overall response (BOR) will be summarized by response category (CR, CRu, PR, SD, PD, Non-evaluable, and not reported).
- BICR-assessed time to response (TTR) will be analyzed using the KM methodology.
- BICR-assessed DOR will be summarized for participants who achieve PR, CRu or CR using the Kaplan-Meier product-limit method. Median values of DOR, along with two-sided 95% CIs (based on the log-log transformation) and range, will also be calculated.
- The BICR-assessed PFS assessment will be summarized descriptively using the Kaplan-Meier (KM) product-limit method. Median values of PFS, along with two-sided 95% CIs (based on the log-log transformation), will also be calculated.
- The OS curves will be estimated using the Kaplan-Meier (KM) product-limit method. Two-sided, 95% confidence intervals for median OS will be constructed based on a log-log transformed CI for the survivor function $S(t)$.

To study the effect of steroid use at baseline, objective response status (responder vs non-responder) may be modeled by a logistic regression with baseline steroid use as a continuous variable. For PFS and OS, a Cox proportional hazards model with baseline steroid use as a continuous variable may be applied.

7.5.4 *Interim Analysis*

Not applicable.

7.6 *Safety*

A subset of tables and listings from the Core Safety SAP will be analyzed. Details will be included in the DPP.

7.6.1 *Deaths*

See Core Safety SAP.

7.6.2 *Serious Adverse Events*

See Core Safety SAP.

7.6.3 *Adverse Events Leading to Discontinuation of Study Therapy*

See Core Safety SAP.

7.6.4 *Adverse Events Leading to Dose Modification*

See Core Safety SAP.

7.6.5 *Adverse Events*

See Core Safety SAP.

7.6.6 *Select Adverse Events*

See Core Safety SAP.

7.6.7 *Immune Modulating Medication*

See Core Safety SAP.

7.6.8 *Multiple Events*

See Core Safety SAP.

7.6.9 *Other Events of Special Interest*

7.6.10 *See Core Safety SAP. Immune-Mediated Adverse Events*

See Core Safety SAP.

7.6.11 *Laboratory Parameters*

The analysis population for each laboratory test is restricted to treated participants who underwent that laboratory test.

7.6.11.1 *Hematology*

See Core Safety SAP.

7.6.11.2 *Serum Chemistry*

See Core Safety SAP.

7.6.11.3 *Electrolytes*

See Core Safety SAP.

7.6.11.4 *Additional Analyses*

See Core Safety SAP.

7.6.12 *Vital Signs and Pulse Oximetry*

See Core Safety SAP.

7.6.13 *Immunogenicity Endpoints*

See Core Safety SAP

7.6.14 *Pregnancy*

See Core Safety SAP.

7.6.15 *Adverse Events by Subgroup*

See Core Safety SAP.

7.7 *Pharmacokinetics*

The listing of concentration of nivolumab in CSF and in serum will be provided in CSR.

The nivolumab concentration data in serum or in CSF obtained in this study may be combined with data from other studies in the clinical development program to develop or refine a population PK model. This model may be used to evaluate the effects of intrinsic and extrinsic covariates on the PK of nivolumab and to determine measures of individual exposure (such as steady-state peak, trough, and time-averaged concentration). In addition, model determined exposures may be used for exposure-response analyses. Results of population PK and exposure response-analyses would be reported separately outside of the study CSR.

7.9 Outcomes Research Analyses

The outcome research analyses will be performed using all outcome research participants.

7.9.1 *EQ-5D-3L questionnaire*

Participant's overall health state on a visual analog scale (EQ-VAS) at each assessment time point and change from baseline will be summarized using descriptive statistics (N, mean, SD, median, 25th and 75th percentiles, minimum, maximum) by cohort.

Proportion of participants reporting problems for the 5 EQ-5D dimensions at each assessment time point will be summarized by level of problem by cohort. Percentages will be based on number participants assessed at assessment time point. EQ-5D questionnaire completion rate, defined as the proportion of questionnaires actually received out of the expected number (i.e., number of participants on treatment or in follow up), will be calculated along with reason for the questionnaire not completed and summarized for each assessment time point by cohort. A by-participant listing of EQ-5D with the problem levels for each of the 5 dimensions (mobility, self-care, usual activities, pain/discomfort and anxiety/depression), health state (5 dimensions digits combined in a 5-digit number) and EQ-VAS will be provided.

7.9.2 *EORTC-QLQ-C30*

Baseline measures will be summarized using descriptive statistics (N, mean, standard deviation, median, first and third quartiles, minimum, maximum) for each QLQ-C30 item, as well as global and functional scales by cohort, based on participants with a baseline measurement.

Post-baseline time point measures and change from baseline will be summarized using descriptive statistics (N, mean, standard deviation, median, first and third quartiles, minimum, maximum) for global, functional, and symptom scales at each assessment time point by cohort. This analysis will be performed in participants who have an assessment at baseline and at least one on-study assessment.

EORTC-QLQ-C30 questionnaire completion rate, defined as the proportion of questionnaires actually received out of the expected number (i.e., number of participants on treatment or in follow up), will be calculated along with reason for the questionnaire not completed and summarized for each assessment time point by cohort.

A by-participant listing containing all single items on the questionnaire, five functional scales, global health status, and nine symptom scales will be provided.

7.9.3 EORTC-QLQ-BN-20

Baseline measures of the transformed scales will be summarized using descriptive statistics (N, mean, standard deviation, median, first and third quartiles, minimum, maximum) for 4 domains and 7 single items by cohort, based on participants with a baseline measurement.

Post-baseline measures and change from baseline of the transformed scales will be summarized using descriptive statistics (N, mean, standard deviation, median, first and third quartiles, minimum, maximum) for 4 domains and 7 single items at each assessment time point by cohort. This analysis will be performed in participants who have an assessment at baseline and at least one on-study assessment.

EORTC-QLQ-BN-20 questionnaire completion rate, defined as the proportion of questionnaires actually received out of the expected number (i.e., number of participants on treatment or in follow up), will be calculated along with reason for the questionnaire not completed and summarized for each assessment time point by cohort.

A by-participant listing containing all single items on the questionnaire, four functional domains, and seven single items will be provided.

8 CONVENTIONS

The following conventions may be used for imputing partial dates for analyses requiring dates:

For missing and partial adverse event onset dates, imputation will be performed using the Adverse Event Domain Requirements Specification¹⁰. Missing and partial Non-Study Medication Domain dates will be imputed using the derivation algorithm described in BMS Non-Study Medication Domain Requirements Specification¹¹.

For death dates, the following conventions will be used for imputing partial dates:

If only the day of the month is missing, the 1st of the month will be used to replace the missing day. The imputed date will be compared to the last known alive date and the maximum will be considered as the death date.

- If the month or the year is missing, the death date will be imputed as the last known alive date.
- If the date is completely missing but the reason for death is present the death date will be imputed as the last known alive date.

For date of progression, the following conventions will be used for imputing partial dates:

- If only the day of the month is missing, the 1st of the month will be used to replace the missing day.
- If the day and month are missing or a date is completely missing, it will be considered as missing.
- In case, the date of death is present and complete, the imputed progression date will be compared to the date of death. The minimum of the imputed progression date and date of death will be considered as the date of progression.

For other partial/missing dates, the following conventions will be used:

- If only the day of the month is missing, the 15th of the month will be used to replace the missing day.
- If both the day and the month are missing, “July 1” will be used to replace the missing information.
- If a date is completely missing, it will be considered as missing.

The following conversion factors will be used to convert days to months or years:

$$1 \text{ month} = 30.4375 \text{ days} \text{ and } 1 \text{ year} = 365.25 \text{ days}$$

Duration (e.g. time from first diagnosis of RCC to first dosing date, duration response, and time to response) will be calculated as follows:

$$\text{Duration} = (\text{Last date} - \text{first date} + 1)$$

All statistical analyses will be carried out using SAS (Statistical Analysis System software, SAS Institute, North Carolina, USA) unless otherwise noted.

Safety conventions from Programming may be summarized separately in an appendix.

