Overall Survival (OS): defined as the time between the first dosing date and the date of death. Participants who are alive at the time of analysis will be censored at last known alive date (LKAD). The overall survival rate at time T is defined as the probability that a subject is alive at time T following first dosing date.

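### SAP section 8 ignores a recorded year of death when the month is missing, so a death recorded in a year after the last known alive date is placed in a year the record rules out

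*SAP*

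**What the plan says.** SAP section 8 (Conventions) gives three rules for incomplete death dates.

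- Day missing: "If only the day of the month is missing, the 1st of the month will be used to replace the missing day". A safeguard follows: "The imputed date will be compared to the last known alive date and the maximum will be considered as the death date".
- Month or year missing: "If the month or the year is missing, the death date will be imputed as the last known alive date". There is no comparison step and no use of a recorded year.
- Whole date missing: "If the date is completely missing but the reason for death is present the death date will be imputed as the last known alive date".

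By contrast, for dates other than death, progression, adverse events and non-study medication, the rule that begins "If both the day and the month are missing" substitutes 1 July, so the recorded year is kept.

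The death date feeds three endpoints. OS (SAP 4.2.3) is "defined as the time between the first dosing date and the date of death". In PFS (SAP 4.2.1 and Table 4.2.1-1) death is the event only when there was no earlier progression and no subsequent anticancer therapy. DOR (SAP 4.1) follows the PFS censoring scheme.

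**The concern.** The second rule treats a death known to have occurred in a given year exactly like a death with no date at all. The LKAD is a reasonable early choice when it is compatible with what was recorded. When the recorded year is later than the LKAD year it is not compatible, and a programmer who follows the rule assigns an event date that the case record excludes. The missing-day rule in the same section shows that the authors meant to use the known part of the date and to take the later of two candidates. That logic was not carried over to the missing month.

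At stake is the accuracy of OS, and to a lesser extent PFS and DOR, in cohorts small enough for one death to be visible in a landmark rate. SAP 7.5.2.1 plans PFS rates at 3 and 6 months. SAP 7.5.2.3 allows OS rates at several times from 3 to 36 months.

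**Working it through.** The documents give no count of incomplete death dates and no figure that depends on this rule, so there is no plan figure to reproduce. The check applies the rules literally to assumed dates.

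**Inputs from the documents**
- Death-date rules, duration formula (last date − first date + 1) and 30.4375 days per month: SAP section 8.
- Survival contacts every 3 months, ±14 days, after the second follow-up visit: Protocol Table 5.1-3, footnote b.
- Cohort sizes of 45 (PCNSL) and 20 (PTL): SAP section 5.

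**Step 1: when the conflict arises.** The earliest date compatible with a recorded year Y and the LKAD is max(1 January Y, LKAD).
- LKAD in year Y: the maximum is the LKAD itself. For LKAD 10 March 2018 and death recorded as 2018, both the SAP rule and the maximum give 10 March 2018, so there is no conflict.
- LKAD before year Y: the maximum is 1 January Y. The SAP date is too early by at least (1 January Y − LKAD).

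**Step 2: minimum shortfall, death recorded only as 2018 (assumed LKADs)**

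| LKAD | SAP death date | Earliest possible date | Shortfall of at least |
|---|---|---|---|
| 20 Dec 2017 | 20 Dec 2017 | 1 Jan 2018 | 12 days |
| 5 Nov 2017 | 5 Nov 2017 | 1 Jan 2018 | 57 days |
| 15 Oct 2017 | 15 Oct 2017 | 1 Jan 2018 | 78 days |
| 20 Sep 2017 | 20 Sep 2017 | 1 Jan 2018 | 103 days |

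For comparison, had the third death been recorded as January 2018 with only the day missing, the SAP's missing-day rule would give max(1 Jan 2018, 15 Oct 2017) = 1 January 2018. Losing the month moves the death back 78 days, into the previous year.

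**Step 3: effect on OS for the third case, assuming first dose on 1 May 2017**
- SAP rule: (167 + 1) / 30.4375 = 5.52 months.
- 1 January 2018: (245 + 1) / 30.4375 = 8.08 months.
- Had the death been on 1 July or 31 December 2018: 14.03 or 20.04 months.

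Here the 6-month landmark lies between 5.52 and 8.08, so the subject counts as dead at 6 months although the record shows survival past it.

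**Step 4: how long the gap can be.** If one survival contact is 14 days early and the next 14 days late, they are 3 × 30.4375 + 28 = 119.3 days apart, or about 119 days. For a subject lost to follow-up the LKAD can be older and the gap longer.

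**Step 5: effect of one subject on a landmark rate, ignoring censoring.** PTL: 1/20 = 5.0 points. PCNSL: 1/45 = 2.2 points. The rate moves only if the landmark falls between the SAP date and the corrected date.

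**The case against.** The strongest reply is that the triggering data will be rare and the harm slight. Most of this stands.

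- **Rarity.** Deaths within 100 days of the last dose are collected as serious adverse events and reported within 24 hours of awareness (Protocol 6.1 and 6.1.1). Survival contact is then 3-monthly, and sites must try to obtain the date of any death they learn of (Protocol 3.6.2). A death that counts for PFS or DOR occurs before documented progression or further therapy, typically under scheduled imaging, where an unknown month is less likely still. Nothing in the documents shows that the number of cases exceeds zero. However, Protocol 3.6.2 also sends sites to public registries for subjects who are lost, which is where an old LKAD and an incomplete death date could meet.
- **Direction.** Times are shortened, so the error cannot flatter nivolumab.
- **Endpoint rank.** BICR-assessed ORR, the primary endpoint, uses no death date. OS and PFS are secondary and descriptive, with no comparison or power attached.
- **Consistency.** The SAP also discards a year-only progression date. But it treats that date as missing and does not assign one that contradicts the record, so this parallel is weak.
- **Permissive wording.** Section 8 opens with "The following conventions may be used for imputing partial dates for analyses requiring dates". This does not help: the lead-in to the death-date rules is mandatory and no alternative is offered.

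A reader might infer that OS and PFS are shortened for every death with a missing month, or that 5 and 2.2 points are expected biases. The documents support neither. When the death falls in the LKAD year there is no conflict, PFS and DOR are reached only when death is the event, and the landmark figures describe one hypothetical subject who meets every condition.

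**Conclusion.** The point holds, within limits. As written, the rule assigns an impossible date when the month of death is missing, the year is known, and that year is later than the LKAD year. No other section of the SAP or protocol overrides it.

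OS is shortened for every such death. PFS and DOR are shortened only where death is the event, with no prior progression and no subsequent therapy. The minimum shortfall is 12 to 103 days in the assumed examples. The number of affected deaths is not given and is probably small.

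This does not threaten the trial's main conclusion. The bias is conservative and ORR is unaffected. It is a low-priority correction, worth making because event dates in a descriptive survival analysis should not contradict the record.

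**What to change.** In SAP section 8, replace the rules for a missing month, a missing year and a completely missing death date with:

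> If the month is missing and the year is known (whether or not the day is recorded), impute 1 January of that year, compare with the last known alive date, and use the maximum. If the year is missing or the date is completely missing, use the last known alive date.

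This extends the SAP's own missing-day logic. It gives the earliest date that the recorded year and the LKAD allow, so it removes the contradiction. It does not remove the early bias, because 1 January is itself the earliest choice, so the SAP's conservative direction is kept.

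The cost is a small edit to the SAP and one line of code, with no new data. It is best settled before the analysis is run.
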